The effectiveness and safety of the early follicular phase full-dose down-regulation protocol for controlled ovarian hyperstimulation: a randomized, paralleled controlled, multicenter trial

2018-12-29

Background

Since the first “tube baby”, Louise Brown, was born in the United Kingdom in 1978, many infertile couples have been benefitted from in vitro fertilization and embryo transfer (IVF-ET) and intracytoplasmic sperm injection (ICSI). It is reported that there are over 5 million babies born with the help of assisted reproductive technology (ART). According to the 2015 national data published by Human Fertility and Embryology Authority (HFEA, 48,147 women received 61,726 IVF/ICSI cycles and gave birth to 17,041 newborns [1]. In the United States, 169,602 IVF/ICSI cycles were performed in 2014 and 68,791 tubal babies were born [2]. China has a huge population base, and therefore has a substantial number of infertile couples. Although a late starter, China is developing rapidly in ART and playing a more and more important role in the area of reproductive medicine.

In spite of the continuous development in ART, so far, the overall success rate of IVF/ICSI is still hovering around 25-40%. The live birth rate per stimulated cycle is 25.6% in the UK in 2015, fluctuating from 1.9% in women aged 45 and elder to 32.2% in women younger than 35 years old [1]. The IVF/ICSI success rate in 2014 in the US is similar [2]. In China, according to the data submitted by 115 reproductive medicine centers on the ART data reporting system developed by Chinese Society of Reproductive Medicine, the delivery rate is about 40% [3]. Hence, there is much room for improvement regarding the live birth rate of IVF/ICSI, which is of great significance to infertile couples.

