There are many factors influencing the success rate of IVF/ICSI, e.g. the infertile couples' age, the controlled ovarian hyperstimulation (COH) protocol, the quality and number of embryos for transferring, the endometrium and luteal phase support protocol, etc. Among them, an appropriate COH protocol is directly associated with the number of oocyte retrieved, as well as the number and quality of embryos, which exert an important influence on the success rate of IVF/ICSI. The luteal phase pituitary down-regulation protocol is one of the most widely used COH protocols in clinical practice, particularly in China. In this protocol, gonadotropin releasing hormone agonist (GnRHa) administered in the previous luteal phase induces a state of down regulation of the pituitary gland via competitive occupying and further exhausting the GnRH receptors in the pituitary, which inhibits the endogenous luteinizing hormone (LH) peak and avoid spontaneous ovulation, decreasing the cycle cancellation rate. But the classic down-regulation protocol may lead to an increased incidence of ovarian hyperstimulation syndrome (OHSS), as well as a negative impact on endometrial receptivity due to the progesterone elevation after multiple oocytes development [4]. The coping strategy is to freeze all the embryos and transfer in the next cycle. Though avoiding the above-mentioned adverse effects, such strategy increases the time to pregnancy (TTP) and therefore results in certain psychological and economic burdens for infertile couples.

In recent years, some Chinese researches applied the early follicular full-dose down-regulation protocol that is always performed to women with endometriosis to a more general IVF/ICSI population and found a clinical pregnancy rate of 64% in the fresh embryo transfer cycle, much higher than that of the luteal phase down-regulation protocol [5-10]. The possible mechanism is that it may improve the down regulation of LH and the endometrial receptivity, therefore having a

better control of LH during COH, increasing the endometrial thickness on hCG day, as well as the embryo implantation rate and clinical pregnancy rate. Furthermore, since this protocol decrease the risk of progesterone elevation on hCG day, it increases the fresh embryo transfer rate and shortens TTP.

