For those not receiving a fresh embryo transfer (e.g. due to OHSS), and those not achieving live birth and with surplus cryopreserved embryos, the outcome of frozen-thawed embryo transfer cycles will be followed up and recorded as well.

Outcome measurements

Primary outcome

The primary outcome of this study is live birth rate per transferred cycle, defined as delivery of any viable infant ≥ 28 gestational weeks divided by all transferred cycles.

Secondary outcomes

Secondary effectiveness endpoints will include implantation rate, biochemical pregnancy, clinical pregnancy and ongoing pregnancy. *Biochemical pregnancy* will be achieved if serum β -hCG ≥ 10 U/L. *Clinical pregnancy* is defined as the presence of an intrauterine gestational sac 28 ± 4 days after embryo transfer. Ongoing pregnancy is defined as a viable pregnancy at 10-12 gestational week. The safety endpoints will include moderate and severe OHSS, pregnancy loss, pregnancy complications, neonatal birth weight and adverse fetal outcomes (e.g. malformation, intrauterine fetal death, etc.)

Statistical analysis

Sample size and power calculation

Sample size will be calculated based on superiority test. The significance level will be set at $\alpha = 0.05$ and the statistical power will be set as $1 - \beta = 0.80$. The reported live birth rate is about 30%, while the live birth rate of the prolonged protocol is predicted to be around 40% based on previous retrospective studies. We set the delta value as 6%, and the ratio between groups will be 1:1; therefore, the sample size of each group is 851. Taking into consideration a drop rate of 10%, we expect to ultimately have a total of 1892 enrollees, with 946 participants in each group.

Statistical analysis method

1. Statistical description: We will adopt descriptive statistical analysis to summarize the participants' demographic characteristics, physical examination, laboratory tests, other health information and the outcome indicators. The continuous variables will be described with means and standard deviation (or median and interquartile range), while the categorical variable will be described with frequency and percentage. The proportion of drop-off cases will be calculated and analyzed.

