2. Comparable analysis It will be used to compare the demographic and other baseline characteristics to make sure the comparability of the two groups. If the continuous variables follow the normal distribution, t test will be performed; if not, the rank sum

test or a normal transformation will be performed. For the categorical variables, chi-square test or Fisher's exact test will be performed.

3. Statistical analysis for the outcome measures Between-group differences for categorical and continuous outcome variables will be assessed by logistic regression and linear regression, respectively.
4. Safety analysis: Adverse events and reaction will be listed and analyzed using the chi-square test.
5. The analysis for the primary outcome and important outcome measurements will be based on both the intention-to-treat analysis and per-protocol analysis. The results of these two analyses will be compared in the final analysis.

Reference

- [1] The United Kingdom national data. Human Fertility and Embryology Authority. 2015
- [2] The United States national assisted reproductive technology(ART) data. Centers for Disease Control and Prevention.2015
- [3] Chinese Reproductive Medicine Society national assisted reproductive technology (ART) data. 2015
- [4] L Hu, Y Sun. The impact of various controlled ovarian hyperstimulation (COS) protocols on the outcome of in vitro fertilization and embryo transfer (IVF-ET). *Journal of Practical Obstetrics and Gynecology*. 2014;30(10):723-725.
- [5] Y Hu, T Ding, Y Zhao, Q Wu. The comparison of the birth outcome of in vitro fertilization and embryo transfer (IVF-ET) after two different down-regulation protocols. *Maternal and Child Health Care of China*.2017;32(4):808-810.
- [6] D Xu, Q Wu. The comparison of the application of ultra-long down-regulation protocol and antagonist protocol in in vitro fertilization and embryo transfer (IVF-ET). *Jiangxi Medical Journal*. 2015;50(1):13-15.
- [7] Q Su, Q Wu, L Tian, Y Li. The clinical analysis of different controlled ovarian hyperstimulation (COS) protocols in in vitro fertilization and embryo transfer (IVF-ET). *Jiangxi Medical Journal*. 2014;49(8):723-725.
- [8] Y Li, Q Wu, Y Yi. The impact of the follicular phase ultra-long long down-regulation protocol on PCOS patients' outcome after in vitro fertilization and embryo transfer (IVF-ET). *Jiangxi Medical Journal*. 2014;49(2):117-120.

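### No baseline covariate and no effect measure are prespecified for the outcome regressions; baseline data enter inference only through tests that cannot establish comparability

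*Combined protocol and SAP*

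**What the plan says.** All references are to the combined protocol and SAP.

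- **Outcome model.** Statistical analysis method, item 3, reads in full: "Between-group differences for categorical and continuous outcome variables will be assessed by logistic regression and linear regression, respectively". It gives no covariates, no rule for choosing them and no effect measure. No other section supplies them.
- **Baseline data.** Item 1 summarises them descriptively. Item 2 tests them between arms (t, rank sum, chi-square or Fisher's exact test): "It will be used to compare the demographic and other baseline characteristics to make sure the comparability of the two groups". It does not say what follows a significant result.
- **Prognosis.** The Background says "There are many factors influencing the success rate of IVF/ICSI" and puts the couple's age first in its list of examples. It also cites UK live birth rates "fluctuating from 1.9% in women aged 45 and elder to 32.2% in women younger than 35 years old".
- **Data already in hand.** Age, basal FSH, E2, AMH and AFC are needed to judge eligibility (Inclusion criteria). BMI sets the starting-dose band (Interventions).
- **Randomization.** 1:1 through a central system, stratified by hospital. Data analysts are blinded.
- **Planning figures.** Sample size and power calculation works in absolute rates: about 30% against about 40%, a delta of 6%, and 851 per group before drop-out.

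**The concern.** Three gaps meet in items 2 and 3.

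First, information that could sharpen the live-birth comparison is collected anyway but has no planned role in the model.

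Second, the baseline tests answer a question that randomisation has already settled. Among all randomised women, a baseline difference between arms is a chance difference. A significant test therefore does not show that the arms are incomparable, and a non-significant one does not show that they are comparable. Because the plan neither lists covariates nor says what a significant test leads to, the content of the primary model can still be chosen after the baseline tables have been seen.

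Third, the sample size is planned on absolute differences, whereas a logistic model yields an odds ratio by default. The plan does not say on which scale the treatment effect will be reported.

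At stake are a little precision and, more importantly, a primary analysis that is fixed in advance.

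**Working it through.** **Inputs.** From Sample size and power calculation: alpha 0.05 (sidedness not stated; two-sided used here), control rate 30%, predicted rate 40%, delta 6%, 851 per group, 10% drop-out. The plan does not say whether the 6% is a detectable difference or a margin; it is read here as 30% v 36%. The documents give no prognostic strength for the covariates. The share of outcome variance explained (R²) is therefore an assumption, taken from 0.9% to 6.9%.

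**The plan's own figure.** The drop-out step reproduces: 851 / 0.90 = 945.6, so 946 per group and 1,892 in total. The 851 does not follow from the stated inputs. The usual two-proportion formula at 80% power gives 963 (two-sided) or 759 (one-sided) for 30% v 36%, and 356 or 281 for 30% v 40%. Nothing below depends on how 851 was reached; it is used as the planned size.

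**Unadjusted power at 851 per group.** Power = Φ{[√n·d − 1.96·√(2p̄(1−p̄))] / √(p₁(1−p₁) + p₂(1−p₂))}.

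For 30% v 36%: d = 0.06, p̄ = 0.33, √851 × 0.06 = 1.750, √(2 × 0.33 × 0.67) = 0.665, √(0.21 + 0.2304) = 0.664. So (1.750 − 1.303) / 0.664 = 0.674, and Φ(0.674) = 75.0%.

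**Power with adjustment.** Replace n by n / (1 − R²).

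| Assumed R² | Effective n per group | Power, 30% v 36% | Power, 30% v 40% |
|---|---|---|---|
| 0 | 851 | 75.0% | 99.1% |
| 0.9% | 859 | 75.3% | 99.2% |
| 5.0% | 896 | 77.1% | 99.4% |
| 6.9% | 914 | 77.9% | 99.4% |

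**Check by simulation.** 4,000 trials per setting, 851 per group, 30% v 36%, logistic regression without and with one composite baseline score:

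| Odds ratio per SD of score | R² | Unadjusted | Adjusted |
|---|---|---|---|
| 1.22 | 0.8% | 74.8% | 75.4% |
| 1.35 | 1.8% | 75.0% | 76.3% |
| 1.65 | 4.8% | 74.9% | 77.4% |

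This agrees with the formula: gains of about 0.6 to 2.5 points.

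**Baseline tests.** With m independent tests at 0.05 under perfect randomisation, the chance of at least one p < 0.05 is 1 − 0.95^m:

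- m = 6 (age, FSH, E2, AMH, AFC, BMI): 1 − 0.735 = 26%
- m = 10: 1 − 0.599 = 40%
- m = 20: 1 − 0.358 = 64%

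The plan does not give m. Correlation among the variables lowers these figures.

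**Effect scale.** At 30% v 40% the odds ratio is (0.4/0.6) / (0.3/0.7) = 1.56, the risk ratio 0.4/0.3 = 1.33 and the risk difference 10 points. At 30% v 36% the unadjusted odds ratio is (0.36/0.64) / (0.30/0.70) = 1.31. In the simulation settings the covariate-adjusted (conditional) odds ratio for the same marginal rates was 1.32 to 1.33. The odds ratio thus depends on which covariates are in the model, so the effect measure needs to be named with them.

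**The case against.** The strongest reply is that nothing here threatens validity. Comparing all randomised women without covariates gives a sound test and a sound estimate, and at the protocol's own predicted 30% v 40% power is already 99.1%. That stands, and it limits the weight of the point.

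Several stronger readings are tempting, and the documents do not support them:

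- *The sponsor chose an unadjusted analysis and an odds ratio alone.* The plan is silent on both covariates and effect measure. Silence is the gap; it is not a decision.
- *The cited age gradient shows that a lot is lost.* The 1.9% figure is for women of 45 and over. The trial enrols women of 20 to 38 with normal ovarian reserve in a first cycle, so the prognostic spread is narrower. The Background lists age as a factor without stating a strength for this population. No section says that AMH, AFC or BMI predicts live birth; proposing them rests on their being measured already and on the judgement that they may be prognostic.
- *The comparability check is likely to fail.* With the six variables named above the chance is 26%, and with ten it is 40%, both below even odds and both assuming independence.
- *A significant baseline test will change the model.* No section says so. The plan leaves the possibility open, and blinding of the analysts reduces the risk without removing it.

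There is also a limit on the other side. The statement that baseline differences are chance holds for all randomised women. The primary outcome is counted per transferred cycle, a set formed after randomisation, where balance is not guaranteed. Item 2's tests do not repair that, and covariate adjustment does not cure it either.

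**Conclusion.** The point holds as a low-cost improvement. The plan prespecifies neither covariates nor an effect measure for its outcome regressions, and its one inferential use of baseline data cannot do what item 2 asks of it.

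The gain in power is modest: from 75.0% to between about 75.3% and 77.9% at 30% v 36%, and from 99.1% to at most 99.4% at 30% v 40%. These figures rest on 851 analysed women per group, a two-sided 0.05 test and an assumed R² of 0.9% to 6.9%, for which the documents give no basis. The better reason to act is that the primary model and its effect scale would be settled before any baseline comparison is seen. No bias in an unadjusted comparison of all randomised women is claimed.

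**What to change.** **Item 3.** Prespecify the primary logistic model with treatment, pre-randomisation age (continuous), AMH, AFC and BMI, and hospital as the stratification factor. From that model report the standardised absolute risk difference with its 95% CI beside the odds ratio. Use the same covariates for the secondary outcomes. Specify BMI as the pre-randomisation value, because its stated use, setting the starting dose, comes after randomisation and down-regulation.

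**Item 2.** Present baseline characteristics by arm descriptively, remove the significance tests, and state that no covariate will be added or dropped because of an observed imbalance.

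**Cost.** Wording in two items of the analysis plan. The variables are already collected for eligibility or dosing, so no extra patients, visits or measurements are needed, provided BMI is recorded before randomisation. Selection into the transferred-cycle denominator has to be dealt with separately.

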 - ② fetal malformation or chromosomal abnormalities;

- ③ intrauterine death.
- 2. Women with a history of one side adnexectomy;
- 3. Women with a poor ovarian response or diminished ovarian reserve (based on Bologna' criteria);
- 4. Women with ovulation dysfunction;
- 5. Women with PCOS (based on Rotterdam's criteria);
- 6. Women with endometriosis;
- 7. Women with the following uterine abnormalities: uterine malformation (unicornuate uterus, uterus bicornis, uterus duplex, mediastinum uterus), adenomyosis, submucosa myoma, intrauterine adhesion;
- 8. Chromosomal abnormality for either or both of the couple;
- 9. Women with contraindications for ART or pregnancy: uncontrolled diabetes mellitus, cardiac disease, undiagnosed liver and/or renal function, vaginal bleeding, suspected or a past history of cervical cancer, endometrial cancer, breast cancer, and a history of deep venous thrombosis, pulmonary embolism, stroke, etc.;
- 10. Women who are enrolled in other clinical trials.

Randomization

After the evaluation, patients met the eligible criteria will be informed, sign the consent form and be included in this study. We will randomly assign women (1:1) to the two groups, using a central randomization system with block sizes of 4 to 6 (changing constantly) and setting hospital as a stratification factor. The researchers (physicians, nurses and embryologists) and patients are not blinded due to the nature of both interventions while the data analysts are blinded.

Interventions

Pituitary down-regulation and controlled ovarian hyperstimulation(COH)

1. *Pituitary down-regulation and starting dose determination*

After inclusion and randomization, qualified participants will be in either intervention or control group and receive one of the following treatments:

1) *Intervention group* (early follicular phase full-dose down-regulation group)

Patients have an injection of 3.75mg long-acting triptorelin acetate (Dipherelin®, IPSEN, France) on the 1st-4th day of menstrual cycle and receive the endocrinology and ultrasound examinations 28-42 days thereafter. If complete pituitary down-regulation is achieved (endometrial thickness≤5mm, basal FSH≤5mIU/mL, LH≤5mIU/mL, E2≤50pg/mL) and the diameter of follicles between 4-6mm under ultrasound, a supplementation of recombinant FSH (Gonal-F®, Merck, Switzerland) will be given according to the participants' BMI (18≤BMI≤22, starting dose 112.5IU/d; 22<BMI≤25, starting dose 150IU/d.

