2) *Control group* (luteal phase long down-regulation group)

Patients have an injection of short-acting triptorelin acetate (Decapeptyl®, Ferring, Germany) 0.1mg every day, 10-12 days before the menstruation and receive the endocrinology and ultrasound examinations 14-21 days thereafter. If complete pituitary down-regulation is achieved (endometrial thickness≤5mm, basal FSH≤5mIU/mL, LH≤5mIU/mL, E2≤50pg/mL) and the diameter of follicles between 4-6mm under ultrasound,

a supplementation of recombinant FSH (Gonal-F®, Merck, Switzerland) will be given according to the participants' BMI ($18 \leq \text{BMI} \leq 22$, starting dose 112.5IU/d; $22 < \text{BMI} \leq 25$, starting dose 150IU/d).

2. *Ovarian response monitoring and gonadotropin dose adjustment:* 4 days after the daily injection of rFSH, the physician will perform ultrasound to monitor the follicular growth, measure the serum hormone level and adjust the dose of exogenous gonadotropins accordingly.

Trigger and oocyte retrieval

1. *hCG trigger for final oocyte maturation:* When the desired follicle size is reached (at least one follicle ≥ 19 mm or two follicles ≥ 18 mm or three follicles ≥ 17 mm), 250 μ g recombinant human chorionic gonadotropin (HCG) (Luveris®, Merck, Switzerland) will be administered subcutaneously.
2. *Oocyte retrieval:* Oocyte retrieval will be performed transvaginally 36-38 hours after pre-ovulatory hCG injection under ultrasound monitoring.
3. *In vitro fertilization and embryo culture:* Oocyte retrieved will be cultured in vitro for 3-6h before being fertilized via IVF or ICSI. Two top-quality Day 3 cleavage embryos will be transferred 72h after retrieval. If more than 15 oocytes are retrieved, the participant should receive ultrasound examination on the day of embryo transfer. For those complaining abdominal or stomach distension, with an ovary ≥ 7 cm in diameter, estradiol ≥ 4500 pg/ml, there is a high risk of developing moderate or severe OHSS, and all the embryos should be frozen.

Embryo transfer and luteal phase support

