Patients will receive luteal phase support with intramuscular progesterone (60mg/day) since the day of oocyte retrieval. On day 3 after oocyte retrieval, two top quality cleavage-stage embryos will be transferred via a catheter under transabdominal ultrasound guidance. The patients will lie in bed for 15 minutes after the procedure. After embryo transfer, 8% progesterone sustained-releasing vaginal gel (Crinone®, Merck, Switzerland) 90mg and dydrogesterone (Duphaston®, AbbottBiologicals, Netherlands) 20mg every day will be used as luteal phase support, continuing for at least 2 weeks. For those who get pregnancy, luteal phase support will be continued to 10 weeks of gestation. The dosage adjustment will be determined by physicians of each study site according to their personal experience.

Pregnancy evaluation and follow-up

All the information will be recorded in our follow-up forms designed specifically for each follow-up visit.

1. *Biochemical determination:* 14 ± 4 days after embryo transfer, serum β -hCG will be tested to determine pregnancy.
2. *Clinical pregnancy determination:* 28 ± 4 days after embryo transfer, a transvaginal ultrasound scan will be performed to confirm the presence of fetal sac, yolk sac and fetal heart.
3. *Ongoing pregnancy determination:* A transvaginal ultrasound scan will be performed at 10-12 weeks of gestation to confirm ongoing pregnancy. The presence of first-trimester pregnancy complications (e.g. OHSS, ectopic pregnancy, miscarriage etc.) will be registered according to the participant's medical record and a telephone follow-up.
4. *28 weeks of gestation:* A telephone follow-up will be conducted to collect the information regarding the second-trimester complications, e.g. pre-eclampsia, gestational diabetes,

prenatal diagnosis, miscarriage, etc.

5. 37 weeks of gestation: A telephone follow-up will be conducted to collect the information regarding the third-trimester complications, e.g. pre-eclampsia, gestational diabetes, preterm birth, etc.
6. *Delivery information:* A telephone follow-up will be made to collect delivery information including gestational age, delivery mode, delivery complications and infant information such as birth weight, any birth defect, etc.
7. *Postpartum information:* Postpartum information includes complications of both the mother and the infant, which will be collected 6 weeks after delivery.

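### The planned comparison of adverse events has no scheduled recording before embryo transfer, so it would miss the down-regulation period in which the arms differ and women who stop before any transfer

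*Combined protocol and SAP*

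**What the plan says.** Safety is a stated aim of the trial, in its title and at the end of the Background. Under *Statistical analysis method*, item 4 reads: "Adverse events and reaction will be listed and analyzed using the chi-square test". It gives no definition of an adverse event, no start or window of collection, no denominator and no analysis set. Item 5 applies intention-to-treat and per-protocol analyses to the primary and important outcomes and does not mention safety.

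Under *Secondary outcomes*: "The safety endpoints will include moderate and severe OHSS, pregnancy loss, pregnancy complications", followed by birth weight and adverse fetal outcomes.

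The section *Pregnancy evaluation and follow-up* opens with "All the information will be recorded in our follow-up forms designed specifically for each follow-up visit" and lists seven items. At item 1, 14 ± 4 "days after embryo transfer, serum β -hCG will be tested to determine pregnancy". Complications first appear at item 3, at 10-12 weeks of gestation, where first-trimester complications, OHSS among them, "will be registered according to the participant's medical record and a telephone follow-up".

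Under *Interventions*, women in the early follicular arm "receive the endocrinology and ultrasound examinations 28-42 days thereafter" and women in the luteal arm "receive the endocrinology and ultrasound examinations 14-21 days thereafter".

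**The concern.** A between-arm test of adverse events is informative only if events are sought over the time when the assigned treatments can cause them, and in the women who received them. As written, the two arms differ in down-regulation: one 3.75 mg depot injection against daily 0.1 mg injections, begun at different points of the cycle and reviewed after different intervals. The FSH starting doses by BMI, the trigger, retrieval, transfer and luteal support are described in the same terms for both arms. The scheduled safety questions begin only after all of this.

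Two things are at stake. Reactions during down-regulation, and the women who stopped because of one, may never reach the adverse event table. And because complications are sought at pregnancy visits, the chance that an event is recorded depends on becoming pregnant, which is what the trial hopes to change. Analysts cannot recover events that nobody asked about.

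**Working it through.** The documents state no adverse event rate and no number of women without a transfer, so there is no planned figure to reproduce. The check is to set every scheduled contact beside its time origin and its stated safety content.

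| Contact | Counted from | Stated safety content |
|---|---|---|
| Down-regulation review | Triptorelin: 28-42 days (intervention), 14-21 days (control) | None; hormones and ultrasound |
| Stimulation scan | 4 days of rFSH | None; ultrasound, hormones, dose adjustment |
| Oocyte retrieval | hCG trigger | None |
| Ultrasound on day of transfer | Only if more than 15 oocytes | OHSS risk (distension, ovary size, estradiol); decides freezing |
| Items 1-2 | Embryo transfer | None; hCG test, pregnancy scan |
| Item 3 | 10-12 weeks of gestation | First-trimester complications, including OHSS |
| Items 4-5 | 28 and 37 weeks of gestation | Later pregnancy complications (item 4: "A telephone follow-up will be conducted to collect the information regarding the second-trimester complications") |
| Items 6-7 | Delivery; 6 weeks after it | Delivery, maternal and infant complications |

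**Who is asked about complications**

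- Stops before retrieval, or has no embryo to transfer: no stated contact.
- All embryos frozen: OHSS risk assessed around the planned transfer, then only the outcome of frozen cycles is promised.
- Fresh transfer, not pregnant: an hCG test, but no stated complication contact.
- Still pregnant at 10-12 weeks: asked from item 3 onward.

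**How dependence on pregnancy can distort the comparison (illustration only)**

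Inputs from *Sample size and power calculation*: 946 women per arm, live birth 30% (control) and 40% (intervention). Assumed: the same true event rate r in both arms, unrelated to pregnancy, with events recorded only in women who reach live birth.

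Women with a live birth: 946 × 0.30 = 284 and 946 × 0.40 = 378. Without: 946 − 284 = 662 and 946 − 378 = 568.

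True events per arm = 946 × r. Recorded events = 946 × live birth rate × r.

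| Assumed r | True, each arm | Recorded, control | Recorded, intervention |
|---|---|---|---|
| 3% | 28.4 | 8.5 | 11.4 |
| 5% | 47.3 | 14.2 | 18.9 |
| 10% | 94.6 | 28.4 | 37.8 |

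At every r the recorded ratio is 0.40 / 0.30 = 1.33, although the true ratio is 1. The illustration overstates the loss, because items 3 to 5 also reach women whose pregnancies fail later. It also applies rates that the plan defines per transferred cycle to all enrolled women. It shows the mechanism and is not a forecast.

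The opposite distortion is equally possible. If one arm has more reactions during down-regulation, and these are not asked about, a real difference disappears from the table.

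**The case against.** The strongest reply is that silence is not absence. The sentence about forms stands under pregnancy follow-up and does not say that these are the trial's only forms. The plan will also summarise physical examinations, laboratory tests and drop-off cases, so other records must exist. Item 3 draws on the medical record, which can reach back before transfer for women who are pregnant. There is a symptom-based OHSS check around transfer. And, apart from OHSS, the named safety endpoints arise in pregnancy or later, where contacts are scheduled.

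Much of this stands, and it limits the point to what the documents specify. It does not remove it. The plan promises a formal test of adverse events and reactions across 14 centres, and none of the records mentioned is given a rule for collecting them before transfer. The medical record is cited only for first-trimester complications. The OHSS check is conditional and serves the decision to freeze.

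A reader might go on to infer more than the documents support:

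- *That no event before transfer would be recorded anywhere.* Clinic visits take place before transfer; what is missing is stated adverse event recording at them.
- *That the arms differ at retrieval.* One procedure is described for both.
- *That the comparison is biased towards no difference.* The illustration produces a spurious difference, so the direction is unknown.
- *That agonist exposure is about twice as long in the intervention arm.* The midpoints are (28 + 42) / 2 = 35 and (14 + 21) / 2 = 17.5 days, a ratio of 2.0. But these are times to review. No stop date is given for the control injections, so total exposure cannot be compared.
- *That a known number of women would have no safety contact.* Any such count needs an assumed percentage without fresh transfer. It would also include freeze-all women, who may have had the OHSS check and whose frozen cycles are followed.

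**Conclusion.** The point holds in this form: the plan commits to a between-arm test of adverse events and reactions but schedules no recording for it before embryo transfer, except a conditional check of OHSS risk. Followed as written, the comparison would leave out the down-regulation period and women who stop before any transfer, and capture would depend on pregnancy. It would be incomplete, with bias possible in either direction.

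The size cannot be stated, because the documents give neither the number of women without a transfer nor any event rate. The conclusion rests on reading the schedule as complete; if separate adverse event forms exist for the treatment phase, the plan should say so, and the gap is then one of description.

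A reader might also conclude that the trial cannot support any safety claim. That goes too far: pregnancy, delivery and neonatal complications may be consequences of the protocol and do have scheduled contacts. What lacks support is a statement about reactions to down-regulation itself. The live birth comparison is unaffected. The change should be made because the gap cannot be filled after the event.

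**What to change.** - Start adverse event recording at the first triptorelin dose for every randomised woman who receives one.
- Add a short adverse event question to visits that already take place: down-regulation review, stimulation scan, retrieval and transfer.
- For women who stop before transfer, add one telephone contact at a fixed time after their last study procedure.
- In item 4 of the analysis section, define an adverse event, the window and the denominator. Analyse per randomised and treated woman, over windows defined the same way in both arms, whether or not transfer or pregnancy follows. For transferred women the window should close at a point reached whether or not they are pregnant; the scheduled hCG test could serve.
- List cancellations due to a reaction by arm.

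The cost is one extra form section, one call for each woman without a transfer, and more minor events to record. No treatment or clinical rule changes.
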